### 12.3 Vital Signs

Vital signs are collected at Screening and at the follow-up/early termination visit. They are also collected within each period at predose and at the completion of all assessments.

Summary statistics (n, mean, SD, minimum, median, and maximum) will be presented for the observed values for systolic and diastolic blood pressure, pulse and respiration rate at each time point by treatment group for the safety population. Summary statistics will also be presented for the change from baseline values to each post baseline time point. In these displays, baseline will be defined as the values that are obtained immediately predose to each treatment.

All vital signs results will be displayed in subject listings.

## 13 PHARMACOKINETIC ANALYSES

### 13.1 General Methods

All PK analyses will be performed using non-compartmental methods in Phoenix® WinNonlin® version 7.0 or higher (Certara Corporation, Mountain View, California, USA). Statistical analyses of PK parameters will be performed using SAS V 9.3 or higher.

Pharmacokinetic blood samples are collected at the end of 5-minute IV infusion and after conclusion of each set of outcome measure tests at approximately 30 minutes, 1 hour, 1 hour 30 minutes and at 2 hours after the start of IV infusion. Blood samples for Cohort 2 (if selected dose is 2 mg) will be at the end of 15-minute IV infusion and after conclusion of each set of outcome measure tests at approximately 40 minutes, 1 hour and 10 minutes, 1 hour 40 minutes, and at 2-hours and 10 minutes after the start of IV infusion.

#### Parameter Definitions

C max	observed maximum concentration
T max	time of observed maximum concentration
AUC t	area under the concentration–time curve from time zero to the last measurable concentration estimated by linear trapezoidal method
AUC ∞	area under the concentration–time curve from time zero extrapolated to infinity, calculated as $AUC_{\infty} = AUC_t + C_t/\lambda_z$ , where C t is the last measurable drug concentration and $\lambda_z$ is the elimination rate constant
%AUC extrap	area under the concentration–time curve extrapolated from the last measurable concentration to infinity as a percentage of AUC ∞
$\lambda_z$	elimination rate constant estimated as the slope of log concentration vs time in the terminal phase of the concentration-time profile
t 1/2	elimination half-life estimated as $0.693/\lambda_z$

The following methods will be utilized for analysis of PK data:

- The exact time of sample collection will be used for PK calculations and for individual subject graphs.
- The scheduled time of sample collection will be used in the summary statistics for concentration results and in mean graphs.
- Pre-dose sampling times will be set to a time value of zero.
- Concentration-dependent PK parameters will be reported in the same units as the assay results.
- Lambda z ( $\lambda_z$ ) will be estimated if a given subject has >2 concentration values in the terminal portion of the curve and will be reported if  $r^2$  (goodness of fit) >0.80.
- The values included in the regression analyses will be determined by WinNonlin and will be reviewed by the pharmacokineticist.
- No value for  $\lambda_z$ ,  $AUC_{inf}$ ,  $\%AUC_{extrap}$ , or  $t_{1/2}$  will be reported for cases where a valid estimate of  $\lambda_z$  is not obtained.
- When  $AUC_{inf}$  and  $\%AUC_{extrap}$  exceeds 20%, values will be flagged in the patient listing.
- All plasma concentrations below the limit of quantitation (BLQ) for the assay prior to the first quantifiable concentration following each dose will be treated as “0” in the PK analyses (and for summary statistics). All BLQ plasma concentrations after the first quantifiable concentration following each dose will be treated as “missing” in the PK analyses, however, for summary statistics, BLQ plasma concentrations will be set to zero.

The following methods will apply for graphical presentation and calculation of summary statistics for individual concentrations and/or PK parameters:

- For concentrations, individual subject data for the time point must be collected within  $\pm 10\%$  of the scheduled protocol time (within 1 minute for the first time point). If more than half of the individual subject’s collection time varies from this guideline, appropriate model predicted values may be used for the calculation of summary statistics for individual concentrations.
- For concentrations, at least half of the individual subject data for the time point must have quantifiable measurements. If fewer than half of the subjects have quantifiable measurements at a given time point, the summary statistics will be reported as not calculated.
- For a given PK parameter, at least half of subjects must have estimable values; otherwise descriptive statistics for the given parameter will be reported as not calculated.

## 13.2 Summary Statistics

Summary statistics (n, arithmetic mean, SD, percent coefficient of variation [%CV], minimum, median, and maximum) will be presented for ERX-963 concentrations through the end of the study for the PK population. In addition, summary statistics (n, arithmetic mean, SD, %CV, minimum, median, maximum, geometric mean [converting back to the original units], and %CV

for the geometric mean) will be presented for the PK parameters by ERX-963 dose. All PK data will be displayed in subject listings.

### 13.3 Figures

The following figures will be provided for the concentration data:

- Individual plasma concentration time figures (linear and semi-log)
- Mean plasma concentration time figures (linear and semi-log)
- Additional figures may be presented (e.g. bar chart for PK parameter  $AUC_{inf}$  by dose level)

## 14 EFFICACY ANALYSES

Efficacy Level	Endpoint
Primary	Not Applicable
Secondary	SSS, PGI-I, PVT, One-back test, CGI-I
Exploratory	EEG, Correlations of ERX-963 plasma concentrations to clinical efficacy endpoints (PVT, SSS, One-back test)

A priori, PGI-I and SSS are the efficacy variables expected to have the greatest sensitivity to treatment with [REDACTED].

### 14.1 Psychomotor Vigilance Task (PVT), Stanford Sleepiness Scale (SSS), One-back Task

The PVT, SSS and One-back Task assessments are collected at Screening, and within Periods 1 and 2 for Cohorts 1 and 2, at predose, 15 minutes, 45 minutes, 1 hour 15 minutes and 1-hour 45minutes after the start of study intervention. However, for Cohort 2, if the selected dose is 2 mg, the PVT, SSS and One-back Task assessments will be measured at 25 minutes, 55 minutes, 1 hour 25 minutes and 1 hour 55 minutes after the start of study intervention. Since the duration of administration of a 2 mg dose is ten minutes longer than the duration of administration for lower dose levels, the time points of these tests in the two cohorts are the same when measured from the end of administration – 10 minutes, 40 minutes, 1 hour 10 minutes and 1 hour 40 minutes.

Descriptive statistics will be computed for PVT, SSS, and One-back Task (n, mean, SD, minimum, median, and maximum) by treatment group.

For each PVT, SSS, and One-back Task efficacy variable, data will be reported for the predose baseline and each time point of the study period. Change from baseline will be summarized for each time point of the study period by treatment. In addition, the median response over time will be found for each subject and then an average will be computed by treatment.

Treatment effects will be declared to be statistically significant at the alpha level of 0.05 and sequence effects will be declared to be statistically significant at the alpha level of 0.10.

Nominal measurement time points will be used for all analyses.

For PVT and SSS, plots of change from baseline at each measurement timepoint for each treatment will also be provided along with plots of individual patient data.

## 14.2 Psychomotor Vigilance Task (PVT)

For PVT, three variables will be analyzed: the number of attentional lapses, the reciprocal of the longest 10% response time of each trial, and the median reaction time.

Cohort 1 and Cohort 2 data will be combined. Treatments will be analyzed such that there are 4 treatment groups: Placebo in Cohort 1, 1 mg ERX-963, Placebo in Cohort 2, and Selected ERX-963.

A mixed effects model will be used to compare efficacy effects following ERX-963 versus placebo. The change from baseline for each of the three PVT variables will be used in the model as the dependent variable. The model will include cohort, sequence, cohort-by-sequence interaction, treatment, treatment period, predose baseline, measurement time point, measurement time-by-baseline interaction, and measurement time-by-treatment interaction as fixed effects, with subject (within cohort and sequence) as random effect. The test statistic will be based on the treatment effects (experimental versus placebo, averaged across the post-dose measurements), using the equally weighted mean of the Cohort 1 and Cohort 2 treatment effects.

The SAS code will be as follows:

```
Proc mixed data = xxxx;
Class patnum cohort sequence period treatment timept;
Model cfb_effvariable = cohort sequence cohort*sequence treatment period
      baseline timept timept*baseline timept*treatment;
Random patnum(cohort sequence) / subject = patnum(cohort sequence);
Estimate 'ERXvPBO' treatment 0.5 -0.5 0.5 -0.5;
Estimate 'ERXvPBOC1' treatment 1 -1 0 0;
Estimate 'ERXvPBOC2' treatment 0 0 1 -1;
Run;
```

## 14.3 Stanford Sleepiness Scale (SSS)

For SSS, the analysis variable will be the numerical rating of sleepiness. The change from baseline will be used in the model as the dependent variable.

Cohort 1 and Cohort 2 data will be combined. Treatments will be analyzed such that there are 4 treatment groups: Placebo in Cohort 1, 1 mg ERX-963, Placebo in Cohort 2, and Selected ERX-963.

A mixed effects model will be used to compare efficacy effects following ERX-963 versus placebo. The change from baseline will be used in the model as the dependent variable. The model will include cohort, sequence, cohort-by-sequence interaction, treatment, treatment period, predose baseline, measurement time point, measurement time-by-baseline interaction, and measurement time-by-treatment interaction as fixed effects, with subject (within cohort and sequence) as random effect. The test statistic will be based on the treatment effects

(experimental versus placebo, averaged across the post-dose measurements), using the equally weighted mean of the Cohort 1 and Cohort 2 treatment effects.

The SAS code will be as follows:

```
Proc mixed data = xxxx;  
Class patnum cohort sequence period treatment timept;  
Model cfb_effvariable = cohort sequence cohort*sequence treatment period  
      baseline timept timept*baseline timept*treatment;  
Random patnum(cohort sequence)/ subject = patnum(cohort sequence);  
Estimate 'ERXvPBO' treatment 0.5 -0.5 0.5 -0.5;  
Estimate 'ERXvPBOC1' treatment 1 -1 0 0;  
Estimate 'ERXvPBOC2' treatment 0 0 1 -1;  
Run;
```

#### **14.4 One-back Task**

For the One-back Task, the analysis variable will be the change from baseline for the proportion of correct responses. The analyses will be done on the arcsine transformation of the square root and the tables will contain the results transformed back to the original scale.

Cohort 1 and Cohort 2 data will not be combined as the difficulty level of the test is different in the two cohorts. There will be two treatment groups in each cohort: ERX-963 and Placebo.

For Cohort 1, only summary statistics (n, mean, SD, minimum, median, and maximum) for the observed data and change from baseline data will be presented.

For Cohort 2, a mixed effects model will be used to compare efficacy effects following ERX-963 versus placebo. The model will include sequence, treatment, treatment period, predose baseline, measurement time point, measurement time-by-baseline interaction, and measurement time-by-treatment interaction as fixed effects, with subject (within sequence) as random effect. The test statistic will be based on the treatment effects (experimental versus placebo, averaged across the post-dose measurements). The comparison in Cohort 2 will be considered the primary comparison for this variable.

The SAS code will be as follows:

```
Proc mixed data = xxxx;  
Class patnum sequence period treatment timept;  
Model cfb_effvariable = sequence treatment period baseline timept  
      timept*baseline timept*treatment;  
Random patnum(sequence)/ subject = patnum(sequence);  
Estimate 'ERXvPBO' treatment 1 -1;  
Run;
```

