#### 9.4.1. Efficacy Analyses

Endpoint	Statistical Analysis Methods
Primary	N/A
Secondary	PVT, SSS, One-back test, CGI-I, PGI-I
Exploratory	Will be described in the statistical analysis plan finalized before database lock.

Descriptive statistics will be computed for PVT, SSS, One-back test, EEG, CGI-I and PGI-I parameters.

For PVT, three variables will be analyzed: the number of attentional lapses, the reciprocal of the longest 10% response time (1/RT) of each trial, and the median reaction time.

For SSS, the analysis variable will be the numerical rating of sleepiness.

For the One-back test, the analysis variable will be the proportion of correct responses (the arcsine transformation of the square root will be used for analysis).

For each PVT, SSS, and One-back test efficacy variable, data will be reported for the pre-dose baseline and each time point of the study period. Differences from pre-dose baseline will be calculated for each time point as well as the median change over the two-hour study period for each participant. Changes from baseline for each patient on [REDACTED] will be compared to their placebo experience.

Cohort 1 and Cohort 2 data will be combined to assess the secondary efficacy parameters.

- A mixed effect model will be used to compare efficacy effects (PVT, SSS, and One-back test) following ERX-963 (IV [REDACTED] vs placebo. The model will include cohort, sequence, cohort-by-sequence interaction, treatment, treatment period, pre-dose baseline, measurement time point, measurement time-by-baseline interaction, and measurement time-by-treatment interaction as fixed effects, with subject (within cohort and sequence) as a random effect. The test statistic will be based on the treatment effects (experimental vs. placebo, averaged across the post-dose measurements), using the equally weighted mean of the Cohort 1 and Cohort 2 treatment effects.
- For CGI-I and PGI-I, the difference between the experimental and placebo responses will be estimated using a model with terms for cohort, sequence, cohort-by-sequence interaction, treatment, and treatment period as fixed effects, and with subject within cohort and sequence as a random effect. The test statistic will be based on the average of the treatment effects in Cohort 1 and Cohort 2.

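### SAP 14.4 plans no ERX-963 versus placebo contrast for One-back within Cohort 1; different task difficulty is a reason not to pool the cohorts, not a reason to omit that contrast

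*SAP*

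**What the plan says.** Protocol 9.4.1 makes no exception for One-back. It states "Cohort 1 and Cohort 2 data will be combined to assess the secondary efficacy parameters", and the model sentence names the test: "A mixed effect model will be used to compare efficacy effects (PVT, SSS, and One-back test". The test statistic is formed "using the equally weighted mean of the Cohort 1 and Cohort 2 treatment effects".

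SAP 14.4 departs from this. It gives the reason, "Cohort 1 and Cohort 2 data will not be combined as the difficulty level of the test is different in the two cohorts", and then says "There will be two treatment groups in each cohort: ERX-963 and Placebo". For the first cohort it plans no model: "For Cohort 1, only summary statistics (n, mean, SD, minimum, median, and maximum) for the observed data" and for change from baseline are to be shown. The mixed model is fitted in Cohort 2, and "The comparison in Cohort 2 will be considered the primary comparison for this variable".

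The rest of the SAP follows the same line. Section 15.3 limits the One-back concentration-response model to Cohort 2, and the mock-up contents label the inferential One-back tables as Cohort 2 only. Protocol 8.1.1 describes a single One-back task and mentions no difficulty levels. The SAP does not identify its approach as a change from the protocol.

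**The concern.** Working memory is part of the secondary objective, and One-back is the only test in the battery that protocol 8.1.1 describes as a memory test. The design is a crossover, so the comparison of interest is each participant's ERX-963 result against that participant's own placebo result. A task that is easier or harder in Cohort 1 than in Cohort 2 changes what the two cohort effects mean relative to each other. It does not by itself invalidate the comparison within Cohort 1, where both periods belong to the same cohort.

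One-back is also the exception among the secondary measures. The SAP code for PVT (14.2), SSS (14.3) and CGI-I/PGI-I (14.5) includes a Cohort 1 contrast, `ERXvPBOC1`; the One-back code has no counterpart.

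At stake is an estimate with an interval for working memory at 1 mg, the dose fixed for Cohort 1. Separate summaries by treatment do not supply it, because they do not give the SD of the within-participant difference.

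**Working it through.** The documents contain no power or precision figure for One-back (SAP 4.3 reports no formal sample size calculation), so there is no stated figure to reproduce. The check sizes what is left out.

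**Inputs**
- At least 6 evaluable participants per cohort (protocol 9.2, SAP 4.3), 3 per sequence (protocol 4.2); an estimated 14 completers in all (protocol 1.1).
- Alpha 0.05 for treatment effects (SAP 14.1); two-sided is assumed, as sidedness is not stated.
- *s*, the SD of the within-participant ERX-963 minus placebo difference on the analysis scale, averaged over the post-dose times. The documents do not give it, so results are in units of *s*.

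**Share outside inference.** 6/12 = 50% at the planned minimum. If 14 complete with at least 6 per cohort, 6/14 = 43% to 8/14 = 57%.

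**One cohort of 6.** With two sequences of 3 and a period effect, SE = (*s*/2) × √(1/3 + 1/3) = *s*/√6 = 0.41 *s*. Residual df are 6 − 2 = 4, or 3 if one is spent on baseline.
- 95% half-width, 4 df: 2.776/√6 = 1.13 *s*
- 95% half-width, 3 df: 3.182/√6 = 1.30 *s*

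These apply equally to the planned Cohort 2 test and to a separate Cohort 1 contrast. With 4 df, 80% power (noncentral t) needs a true effect of about 1.54 *s*, and power at a true effect of 1 *s* is 0.46.

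**Protocol's two-cohort mean, 12 participants, same *s* in both cohorts.** SE = *s*/√12 = 0.29 *s*. Residual df are 12 − 3 = 9 (two treatment effects and a common period effect), or 8 with one more term.
- 95% half-width, 9 df: 2.262/√12 = 0.65 *s*
- 95% half-width, 8 df: 2.306/√12 = 0.67 *s*

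With 9 df, 80% power needs about 0.91 *s*, and power at 1 *s* is 0.87.

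**Comparison.** Cohort 2 alone is wider than the two-cohort mean by a factor of 1.13/0.65 ≈ 1.73 (4 and 9 df) or 1.30/0.67 ≈ 1.95 (3 and 8 df, from unrounded values). The factor therefore depends on the df convention, and both versions assume equal SDs at two difficulty levels.

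**With 7 per cohort.** The half-width is 0.97 *s* for one cohort (5 df) and 0.59 *s* for the two-cohort mean (11 df).

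**The case against.** The strongest reply is that little is lost. Protocol 9.1 says the study is not powered for efficacy, protocol 4.2 calls it exploratory, and SAP 14 names PGI-I and SSS, not One-back, as the measures expected to be most sensitive. A Cohort 1 contrast would detect only effects of about 1.5 SD or more, and it does nothing for the precision of the Cohort 2 test. That stands, and it limits the point to a cheap improvement.

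A second reply is that the protocol never promised a Cohort 1 test. It specifies only the equally weighted mean; the cohort-specific contrasts for the other measures come from the SAP. That also stands. What the SAP drops from the protocol is the two-cohort contrast, and the separate Cohort 1 estimate would be an addition.

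Third, Cohort 1 may be uninformative for a reason not written down, such as scores near ceiling or a change of difficulty between periods. The documents mention neither. If one applies, the SAP should say so.

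A reader might infer more than the documents support:
- *That Cohort 1 One-back data are unused.* They are summarised by treatment, observed and change from baseline (SAP 14.1 and 14.4), and a One-back listing is in the mock-up contents.
- *That there can be no inference at 1 mg.* Protocol 4.1 allows Cohort 2 to receive 1 mg, in which case its model covers that dose, although 2 mg is the planned Cohort 2 dose.
- *That pooling should simply be restored.* This would ignore the stated difference in difficulty.
- *That the restriction followed a look at unblinded Cohort 1 results.* A sponsor-unblinded interim efficacy analysis is planned after Cohort 1 (protocol 9.5, SAP 17), but nothing ties the One-back decision to it.

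The April 2020 memo retains only some secondary outputs and marks removals by highlighting that is not visible in the text available, so which One-back outputs were finally kept cannot be checked.

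**Conclusion.** The point holds in a limited form. Protocol 9.4.1 and SAP 14.4 disagree on the One-back analysis, and the reason given supports separate analysis by cohort but not the absence of a Cohort 1 contrast. This does not look like outdated protocol text: Amendment 2 (31 October 2019) removed EEG from the same model sentence and left One-back in, and the SAP was signed from 6 December 2019.

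The consequence is that about half the participants lie outside One-back inference and, unless Cohort 2 also receives 1 mg, there is no interval estimate for working memory at that dose. The missing estimate would be imprecise, with a half-width of about 1.1 to 1.3 SD at 6 participants. These figures rest on a balanced 3 + 3 allocation and on within-participant differences averaged over time. The two-cohort figures rest further on a common SD, which differing difficulty makes doubtful.

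**What to change.** 1. Fit the SAP 14.4 model separately to Cohort 1 and report the ERX-963 minus placebo contrast with a 95% CI, labelled supporting. If Cohort 1 is considered uninformative, state why instead.
2. Keep Cohort 2 as the primary comparison for One-back.
3. Treat an equally weighted mean of the two within-cohort contrasts as optional and supporting only, with residual variances and baseline slopes allowed to differ by cohort.
4. Reconcile protocol 9.4.1 with SAP 14.4, identify the departure as such, and record when and why the task difficulty changed.

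The cost is one more model run, one table and some wording. The downside is a small, unpowered contrast that may be diluted if Cohort 1 scores are near ceiling. The report should say so, so that a wide interval or a null result is not read as evidence of no effect.

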#### **14.5 Clinical Global Impression – Improvement (CGI-I) and Patient Global Impression – Improvement Scale (PGI-I)**

The CGI-I and PGI-I assessments are collected after the last outcome measure test in each study period.

Descriptive statistics will be computed for CGI-I and PGI-I (n, mean, SD, minimum, median, and maximum) by treatment.

Summary bar charts giving each treatment's distribution of responses will be provided for the GCI-I and PGI-I.

The difference between the experimental and placebo responses will be estimated using a model with terms for cohort, sequence, cohort-by-sequence interaction, treatment, and treatment period as fixed effects, and subject within cohort and sequence as a random effect. The dependent variable in the model will be the assessment. The test statistics will be based on the average of the treatment effects in Cohort 1 and Cohort 2.

The SAS code will be as follows:

```
Proc mixed data = xxxx;  
Class patnum cohort sequence period treatment;  
Model effvariable = cohort sequence cohort*sequence treatment period;  
Random patnum(cohort sequence)/ subject = patnum(cohort sequence);  
Estimate 'ERXvPBO' treatment 0.5 -0.5 0.5 -0.5;  
Estimate 'ERXvPBOC1' treatment 1 -1 0 0;  
Estimate 'ERXvPBOC2' treatment 0 0 1 -1;  
Run;
```

